## **3.3 Analysis Variables**

### **3.3.1 Clinical Efficacy**

Tumor response will be assessed using RECIST v1.1 and irRECIST criteria. When a radiological assessment is unavailable to determine RECIST (irRECIST), a clinical assessment of progressive disease and/or death may be used in lieu of the RECIST (irRECIST) to determine disease response. This combined clinical efficacy endpoint will be used in the primary efficacy analysis. RECIST and irRECIST criteria are described in detail in the protocol, and an abbreviated description is provided below.

RECIST evaluation of target lesions are as follows:

Response	Criteria for Response
Complete Response (CR)	Disappearance of all target lesions
Partial Response (PR)	At least a 30% decrease in the sum of the diameters of target lesions taking as reference the baseline sum diameters
Stable Disease (SD)	Neither sufficient shrinkage to qualify for PR nor sufficient increase to qualify for PD
Progressive Disease (PD)	At least 20% increase in the sum of the diameters of target lesions taking as reference the baseline sum diameters or new lesion identification

irRECIST evaluation of target and new lesions are as follows:

Complete Response (irCR)	Complete disappearance of all target and new, measurable lesions, with the exceptions of lymph nodes which must decrease to < 10 mm in short axis.
Partial Response (irPR)	Decrease in TMTB* $\geq$ 30% relative to baseline.
Stable Disease (irSD)	Not meeting criteria for irCR or irPR, in absence of irPD.
Progressive Disease (irPD)	Increase in TMTB $\geq$ 20% relative to nadir.

\*TMTB = SumD target lesions + SumD new, measurable lesions.

For both RECIST and irRECIST, if CA125 levels are initially above the upper normal limit, they must normalize for a subject to be considered in complete clinical response.

Efficacy variables include:

- Progression-free Survival
  - Proportion of subjects surviving without progression at 6 months (based on RECIST v1.1 and/or clinical progression/death) – Phase 2 primary endpoint
  - Proportion of subjects surviving without progression at 6 months (based on irRECIST and/or clinical progression/death) – Phase 2 secondary endpoint
  - Proportion of subjects surviving without progression at 12 months (based on RECIST v1.1 and irRECIST and/or clinical progression/death) – Phase 2 secondary endpoints
  - Proportion of subjects surviving without progression at 6 and 12 months (based on RECIST v1.1 and irRECIST and/or clinical progression/death) – Phase 1 secondary endpoints
  - Progression-free survival time (based on RECIST v1.1 and irRECIST and/or clinical progression/death) – Phase 1 and 2 secondary endpoints

- Tumor Response
  - Overall Response Rate (ORR) based on RECIST v1.1 and irRECIST and/or clinical progression/death – Phase 1 and 2 secondary endpoints
  - Overall Disease Control Rate – stable disease (SD), PR, or CR over a period of at least 4 weeks based on RECIST v1.1 and irRECIST- Phase 1 and 2 secondary endpoints
- Overall Survival
  - Median overall survival time – Phase 1 and 2 secondary endpoint

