3.1.6 Sample Size and Statistical Considerations

Phase 1 of this trial will employ the 3+3 design as described in Section 3.1.7. The maximum tolerated dose (MTD) is defined as the highest dose for which fewer than 33% of subjects experience a dose-limiting toxicity (DLT).

Phase 2 of this trial will expand the Phase 1 cohort that was treated at the MTD. For the subject population to be enrolled, standard of care treatment with PLD alone has been reported to result in a 25% 6-months PFS rate. (47-50) A true 6-months PFS rate of $\geq 45\%$ in the current study, using motolimod + MEDI4736 with standard of care, would be of interest and represent a clinically meaningful improvement, while $\leq 25\%$ would be of no interest. Therefore, the study will test the hypotheses $H_0: p \leq 0.25$ versus $H_1: p \geq 0.45$, with p being the proportion of subjects who have survived and not progressed at 6 months, based on RECIST v1.1 criteria. Expansion of the Phase 1 MTD cohort to 41 evaluable subjects will yield 80% power to test the null hypothesis of 6-months PFS rate of $\leq 25\%$ against the alternative hypothesis of a PFS rate of $\geq 45\%$ at an alpha level of 0.05 (one-sided) based on exact test for single proportion.

PER Amendment 2, motolimod dosing will be discontinued for all subjects.

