8.5.3.3 Evaluation of Best Overall Response

The best overall response is the best response recorded from the start of the treatment until disease progression/recurrence (taking as reference for progressive disease the smallest measurements recorded since the treatment started). The subject's best response assignment will depend on the achievement of both measurement and confirmation criteria.

C O N F I D E N T I A L

For Subjects with Measurable Disease (i.e., Target Disease)

Target Lesions	Non-Target Lesions	New Lesions	Overall Response	Best Overall Response when Confirmation is Required*
CR	CR	No	CR	≥4 wks. Confirmation**
CR	Non-CR/Non-PD	No	PR	≥4 wks. Confirmation**
CR	Not evaluated	No	PR	
PR	Non-CR/Non-PD/not evaluated	No	PR	
SD	Non-CR/Non-PD/not evaluated	No	SD	documented at least once ≥4 wks. from baseline**
PD	Any	Yes or No	PD	no prior SD, PR or CR
Any	PD***	Yes or No	PD	
Any	Any	Yes	PD	

* See RECIST 1.1 manuscript for further details on what is evidence of a new lesion.
 ** Only for non-randomized trials with response as primary endpoint.
 *** In exceptional circumstances, unequivocal progression in non-target lesions may be accepted as disease progression.
 Note: Subjects with a global deterioration of health status requiring discontinuation of treatment without objective evidence of disease progression at that time should be reported as “*symptomatic deterioration.*” Every effort should be made to document the objective progression even after discontinuation of treatment.

For Subjects with Non-Measurable Disease (i.e., Non-Target Disease)

Non-Target Lesions	New Lesions	Overall Response
CR	No	CR
Non-CR/non-PD	No	Non-CR/non-PD*
Not all evaluated	No	not evaluated
Unequivocal PD	Yes or No	PD
Any	Yes	PD

* ‘Non-CR/non-PD’ is preferred over ‘stable disease’ for non-target disease since SD is increasingly used as an end-point for assessment of efficacy in some trials so to assign this category when no lesions can be measured is not advised.

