### **3.8 Efficacy Analysis**

#### **3.8.1 Progression-free Survival**

The primary endpoint in Phase 2 of this study is the PFS rate at 6 months defined as the visit at the start of Cycle 7, where progression is assessed for subjects based on a combination of RECIST v1.1 and/or the clinician's assessment of clinical progression or death. The primary efficacy analysis will be based on the Per Protocol population. A sensitivity analysis will be conducted on the ITT population. A secondary efficacy analysis will be conducted on the Phase 2 Per Protocol population.

The primary efficacy analysis entails testing the null hypothesis that PFS at 6 months is less than or equal to 25% against the alternative hypothesis that PFS at 6 months is higher for those treated with PLD and MEDI4736 combination. This hypothesis will be tested at  $\alpha=0.05$  using the 90% two-sided confidence interval for the PFS rate at 6 months based on Kaplan-Meier product limit estimates. The null hypothesis will be rejected in favor of the alternative if the lower bound of that confidence interval is greater than 25%. The null hypothesis will also be tested using a one-sided binomial test as a sensitivity analysis. In this analysis, if a subject has no tumor response assessment, or discontinued treatment or withdrew from the study for other reasons, he or she will be considered as "progressed." The null hypothesis will be rejected in favor of the alternative if the lower bound of a two-sided 90% binominal confidence interval is greater than 25%.

Table displays will include PFS rate at 6 months and the corresponding 90% confidence interval along with the corresponding number of subjects at risk. In addition, PFS will be presented graphically.

Secondary efficacy analyses will use the secondary efficacy endpoints listed in section 3.3.1 of the SAP and will be based on the ITT population. PFS rate and the corresponding 95% confidence interval will be calculated based on Kaplan-Meier product limit estimates and will be displayed by cohort and phase.

Descriptive analyses of PFS will include the following:

- Number and percentage of subjects that died or had a confirmed progression,
- Number and percentage of subjects that survived without a confirmed progression,
- Number and percentage of subjects lost to follow up (unknown survival and/or progression status), and
- Number of subjects missing the tumor response assessment

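### The primary 6-month PFS event is defined inconsistently: RECIST v1.1 or death in the protocol, RECIST v1.1 plus clinician-judged progression (optional in one place, unconditional in another) in the SAP

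*SAP*

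**What the plan says.** **Protocol.** Section 3.1.6 tests "the proportion of subjects who have survived and not progressed at 6 months, based on RECIST v1.1 criteria". The objectives table in section 4 and sections 4.1.1.1 and 4.1.2 repeat RECIST v1.1 as the basis of the primary endpoint. A note to the best-overall-response table in 8.5.3.3 adds that subjects who stop because their health worsens "without objective evidence of disease progression at that time should be reported as" symptomatic deterioration, and asks that objective progression still be sought.

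**SAP, RECIST only.** Sections 2.1 and 2.2.3.1 name RECIST v1.1 for the primary 6-month rate.

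**SAP, conditional and optional.** Section 3.3.1 says that when no radiological assessment is available, "a clinical assessment of progressive disease and/or death may be used in lieu of the RECIST (irRECIST) to determine disease response". It states that this combined endpoint goes into the primary analysis.

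**SAP, unconditional.** The endpoint list in 3.3.1 joins RECIST v1.1 and clinical progression by *and/or*. Section 3.8.1 sets the rate at the visit opening Cycle 7, "where progression is assessed for subjects based on a combination of RECIST v1.1 and/or the" clinician's judgement of clinical progression or death. Section 2.2.3.2 dates PFS by the earliest radiological or clinical progression. None of these carries the condition that imaging is unavailable.

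**SAP, confirmed.** The PFS time definition in 3.8.1 requires confirmed progression, clinical or radiological, and does not say how a clinical call is confirmed.

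SAP section 1 says its methods follow protocol Amendment 4. The SAP does not identify the addition of clinical progression as a departure from it.

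**The concern.** The trial is single-arm and open-label, and its primary result is a rate tested against a fixed 25%. Who counts as progressed should be settled before outcomes are known. Scans are scheduled at Days 85, 169 and 253, twelve weeks apart, so a clinician may well call progression between scans or alongside a scan that does not meet RECIST progression. For such a subject the current texts give different answers, and the word *may* in SAP 3.3.1 leaves the answer to be chosen subject by subject. If the observed rate falls near the cut-off, that choice decides whether the null hypothesis is rejected.

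**Working it through.** **1. The rules side by side**, for a subject whom the clinician judges to have progressed:

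| Rule | Cycle 7 scan shows no RECIST progression | No Cycle 7 scan |
|---|---|---|
| Protocol 3.1.6, 4.1.1.1; SAP 2.2.3.1 | Progression-free | No RECIST event |
| SAP 3.3.1, conditional text | Progression-free | Event if the option is used; otherwise censored at the last scan (SAP 3.8.1) |
| SAP 3.3.1 list, 3.8.1 rate, 2.2.3.2, read literally | Event | Event |
| SAP 3.8.1 PFS time | Event only if confirmed (undefined) | Event only if confirmed (undefined) |

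**2. The plan's own figure.** Inputs from protocol 3.1.6: null 0.25 ("standard of care treatment with PLD alone has been reported to result in a 25% 6-months PFS rate"); alternative 0.45; "Expansion of the Phase 1 MTD cohort to 41 evaluable subjects will yield 80% power to test the null hypothesis"; tested "at an alpha level of 0.05 (one-sided) based on exact test for single proportion". The cut-off is the smallest r with P(X ≥ r | n = 41, p = 0.25) ≤ 0.05.
- r = 15: 0.0666, too large.
- r = 16: 0.0333, accepted.
- Power: P(X ≥ 16 | n = 41, p = 0.45) = 0.8225.

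The stated 80% is reproduced, and the exact cut-off is 16 of 41 progression-free.

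**3. The SAP decision rule.** SAP 3.8.1 rejects if the lower bound of the two-sided 90% Kaplan-Meier interval exceeds 25%. With 41 subjects and no censoring before Cycle 7, the estimate is p = x/41 and Greenwood's variance reduces to p(1 − p)/41. The linear-scale bound is p − 1.645 × √(p(1 − p)/41).
- 16/41: 0.3902 − 1.645 × 0.0762 = 0.265. Reject.
- 15/41: 0.3659 − 1.645 × 0.0752 = 0.242. Do not reject.

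The exact (Clopper-Pearson) bounds are 0.262 and 0.241, and the log-log bounds 0.266 and 0.245, with the same decisions. On a plain log scale the bound is p × exp(−1.645 × √((1 − p)/(41p))):
- 15/41: 0.261. Reject.
- 14/41: 0.239. Do not reject.

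The scale moves the switch by one subject but does not remove it.

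**4. One contested subject.** Let 15 others be progression-free and 25 others have events (15 + 25 + 1 = 41).
- Counted as an event: 15/41, linear bound 0.242. Not rejected.
- Counted as progression-free at Cycle 7: 16/41, 0.265. Rejected.
- No Cycle 7 scan, option in SAP 3.3.1 not used, censored at the Day 85 scan: estimate 0.376 to 0.390, linear bound 0.250 (0.2502 before rounding) to 0.265, log-log 0.252 to 0.266. Rejected.

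The third line assumes that the other events fall at the Day 85 and Day 169 scans, in the splits tried from 5/20 to 25/0, and that the contested call comes near Day 120.

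**5. How often the result lies at the boundary.** The binomial probabilities of exactly 15 and exactly 16 of 41 are 7.1% and 9.4% at a true rate of 45%, and 12.2% and 12.7% at 39%. The documents give no rate for contested subjects.

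**The case against.** The strongest reply is that the SAP holds one rule. Section 3.3.1 sets the order (scan first, clinician only when no scan is available), and the *and/or* in its endpoint list and in 3.8.1 is shorthand for that. This is a fair reading, so a reader who infers three irreconcilable rules goes further than the text requires. On that reading the case of a clinical call with a non-progressing scan is settled within the SAP. Three things are not: RECIST-only against combined, the optional *may*, and the undefined confirmation.

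Second, counting clinical progression in addition to RECIST can only lower the PFS rate. A reader might infer that the SAP loosens the endpoint in favour of success; the direction is the opposite. What stands is that an optional rule also permits the events to be left out.

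Third, SAP 3.8.1 already has a binomial sensitivity analysis that counts subjects with no tumor assessment, or who stopped for other reasons, as progressed. That answers most no-scan cases. It is not the primary analysis, and it does not settle a clinical call beside a scan without progression.

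Fourth, any fixed cut-off turns on one subject. That is true; the defect is that this subject's classification is left open.

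Two further inferences are not supported. A reader might build a larger swing by censoring several unscanned subjects at Day 1. SAP 3.8.1 applies that only to subjects with no tumor response assessment, who may fall outside the per-protocol set because it requires disease assessments. A reader might also conclude that the SAP offers no RECIST-only result. Section 2.2.3.1 names RECIST v1.1 and Table 14.2.1.1 is titled accordingly, so the SAP is ambiguous on this. Lastly, the symptomatic-deterioration note in protocol 8.5.3.3 concerns best response and is supporting context only, since it is not a PFS event rule.

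**Conclusion.** The point holds. Current protocol and SAP text give conflicting rules for the primary event, and even on the most charitable reading of the SAP the protocol conflict and the optional wording remain. The size is one subject at the boundary: 16/41 against 15/41 on the linear, log-log and exact bounds, or 15/41 against 14/41 on a plain log scale. This rests on 41 per-protocol subjects, no other censoring before Cycle 7, and an interval scale that the SAP does not name. Away from the boundary a single contested subject changes the estimate but not the decision. Since this is the primary endpoint, it should be corrected before the analysis.

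**What to change.** State one mandatory event rule and use it in SAP 2.2.3.1, 2.2.3.2, 3.3.1 and 3.8.1 (both the rate and the PFS time definition). One workable version: RECIST v1.1 decides whenever an evaluable scan exists for the time point, and a dated clinical progression *will* count as an event when none exists. Other rules could be defended; what matters is that the rule is fixed and the same everywhere. Remove the unconditional *and/or*, define or delete *confirmed*, and say openly that the combined endpoint differs from the protocol's.

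Add a pre-specified sensitivity analysis on the protocol endpoint, RECIST v1.1 progression or death only, in the same per-protocol population.

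The cost is SAP wording and one extra analysis on data already collected. The sample size of 41 and the exact cut-off of 16 are unaffected.

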8.5.3 Response Criteria

8.5.3.1 Evaluation of Target Lesions

Complete Response (CR): Disappearance of all target lesions. Any pathological lymph nodes (whether target or non-target) must have reduction in short axis to <10 mm.

Partial Response (PR): At least a 30% decrease in the sum of the diameters of target lesions, taking as reference the baseline sum diameters

Progressive Disease (PD): At least a 20% increase in the sum of the diameters of target lesions, taking as reference the smallest sum on study (this includes the baseline sum if that is the smallest on study). In addition to the relative increase of 20%, the sum must also demonstrate an absolute increase of at least 5 mm. (Note: the appearance of one or more new lesions is also considered progressions).

Stable Disease (SD): Neither sufficient shrinkage to qualify for PR nor sufficient increase to qualify for PD, taking as reference the smallest sum diameters while on study

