### **3.8.2 Tumor Response**

Tumor response will be summarized and analyzed descriptively for the ITT population.

The number and percentage of subjects meeting criteria of CR, PR, SD, and PD will be displayed. The number and percentage of subjects meeting criteria of CR or PR over a period of at least 4 weeks (Overall Response Rate – ORR) based on RECIST v1.1 and irRECIST, as well as the number and percentage of subjects meeting criteria of SD, PR, or CR over a period of at least 4 weeks (Overall Disease Control Rate – ODCR) will be displayed along with the corresponding 95% binomial CIs. In calculating ORR and ODCR, subjects who drop out prior to meeting the responder criteria will be considered as non-responders. Descriptive statistics will be presented for duration of response, defined as the time from the first response of PR or CR to

the date of disease progression or death. Tumor response and tumor marker CA-125 will be presented in subject listings.

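### The SAP measures RECIST progression from the baseline sum, the protocol from the smallest sum on study; applied as written, the SAP row would count some subjects who shrink and regrow as progression-free at 6 months

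*SAP*

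**What the plan says.** SAP 3.3.1 tabulates the RECIST categories for target lesions. Its progression row reads "At least 20% increase in the sum of the diameters of target lesions taking as reference the baseline sum diameters or new lesion identification". It gives no minimum absolute increase. The table is introduced with the statement that "RECIST and irRECIST criteria are described in detail in the protocol, and an abbreviated description is provided below". In the same section, the irRECIST progression row uses a different reference, an increase of at least "20% relative to nadir".

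Protocol 8.5.3.1 also sets a 20% increase but measures it "taking as reference the smallest sum on study (this includes the baseline sum if that is the smallest on study", and adds that "the sum must also demonstrate an absolute increase of at least 5 mm". Protocol 8.5.3.3 repeats the reference: "taking as reference for progressive disease the smallest measurements recorded since the treatment started". Protocol 8.5.3.4 uses it again for duration of response.

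SAP 3.8.1 defines the Phase 2 primary endpoint as the PFS rate at the start of Cycle 7, where "progression is assessed for subjects based on a combination of RECIST v1.1" and the clinician's assessment of clinical progression or death. SAP 3.8.2 summarizes "duration of response, defined as the time from the first response of PR or CR" to progression or death, so the progression rule enters there too.

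**The concern.** Replacing the smallest sum with the baseline sum changes the rule. After shrinkage, a lesion sum has to climb back to baseline and then a further 20% before the SAP row calls progression. The protocol calls it at 20% above the low point.

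The scan schedule allows this pattern before the primary endpoint. The only on-treatment scan before Cycle 7 (target day 169) is at Cycle 4 (target day 85). The two rules disagree on a subject who shrinks by day 85 and by day 169 regrows to at least 20% and 5 mm above nadir, but stays below 120% of baseline. If she also has no new lesion, no other progression event and has not died, the protocol counts her as progressed and the SAP row as progression-free. The clinical-progression fallback in SAP 3.3.1 does not reach her, because it applies only when no radiological assessment is available.

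The error favors the treatment: it raises the 6-month PFS rate and lengthens PFS time and duration of response. The trial is single-arm and tests against a fixed 25%, so no control group shares the error.

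**Working it through.** **1. Progression thresholds.** Let B be the baseline sum, r the fraction of shrinkage and nadir = B(1 − r). The protocol threshold is the larger of 1.2 × nadir and nadir + 5 mm. The SAP row's threshold is 1.2 × B. For B = 100 mm:

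| Shrinkage | Nadir (mm) | Protocol PD at (mm) | SAP row PD at (mm) | Missed band (mm) | SAP threshold as rise over nadir |
|---|---|---|---|---|---|
| 10% | 90 | 108 | 120 | 108 to <120 | 33% |
| 20% | 80 | 96 | 120 | 96 to <120 | 50% |
| 30% | 70 | 84 | 120 | 84 to <120 | 71% |
| 50% | 50 | 60 | 120 | 60 to <120 | 140% |

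The 5 mm condition is met in every row. Example: 100 mm at baseline, 70 mm at day 85, 90 mm at day 169. From nadir this is +20 mm, 20/70 = +29%, so it is PD under the protocol. From baseline it is −10%, so it is not PD under the SAP row.

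**2. The missing 5 mm condition.** It binds only if 0.2 × reference < 5 mm, that is, for a reference sum below 25 mm. There the omission acts in the opposite direction. With baseline and nadir both 20 mm, a sum of 24.5 mm exceeds the SAP threshold of 24 mm but not the protocol threshold of 25 mm.

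**3. The plan's own test.** Inputs from Protocol 3.1.6: null rate 0.25, alternative 0.45, N = 41, one-sided alpha 0.05, exact test, stated power 80%. P(X ≥ 15 | 41, 0.25) = 0.067 and P(X ≥ 16 | 41, 0.25) = 0.033, so the rule rejects at 16/41 or more. The power is P(X ≥ 16 | 41, 0.45) = 0.823, which meets the stated 80%. The exact one-sided 95% lower limits agree: 0.2408 at 15/41 and 0.2623 at 16/41.

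**4. The SAP's Kaplan-Meier interval.** SAP 3.8.1 makes this the primary method. If nobody is censored before Cycle 7, S = k/41 and Greenwood's standard error is √(S(1 − S)/41). The lower limits of the two-sided 90% interval are:

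| k/41 | S | SE | Linear | Log-log | Excludes 0.25? |
|---|---|---|---|---|---|
| 15/41 | 0.3659 | 0.0752 | 0.2421 | 0.2447 | No |
| 16/41 | 0.3902 | 0.0762 | 0.2649 | 0.2662 | Yes |

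The threshold is again 16/41. The case with censoring was not computed.

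**5. Effect of misclassification (assumed range).** The documents give no frequency for shrinkage followed by regrowth without another event. Let m be the expected number of subjects wrongly counted as progression-free when the true rate is 25%. The chance of rejection is then P(X ≥ 16 | 41, 0.25 + m/41).

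| m | Apparent rate | P(reject) |
|---|---|---|
| 0 | 0.250 | 0.033 |
| 0.25 | 0.256 | 0.041 |
| 0.5 | 0.262 | 0.0498 |
| 1 | 0.274 | 0.072 |
| 2 | 0.299 | 0.135 |

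The planned 0.05 is exceeded once slightly more than half a subject is expected to be misclassified.

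**The case against.** The strongest reply is that the row may never operate. The SAP says that response is assessed by RECIST v1.1, sends the reader to the protocol for the detail, and bases its methods on the protocol. Its endpoint definitions name RECIST v1.1 rather than the table. The flowcharts schedule a RECIST 1.1 assessment at each imaging visit. The SAP lists tumor response by visit but has no lesion-sum listing and no nadir or percent-change variable, which points toward recorded responses. If those are used, no result changes. This stands as a limit on the consequence. It does not make the row correct, because the SAP never states the source. Calling the table abbreviated can cover the missing 5 mm condition, but not a different reference sum.

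The affected group is also narrow, and nothing in the documents supports one or two misclassified subjects rather than a fraction of one. Both points are fair. At half a subject or fewer, the error rate stays within 0.05.

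Finally, the irRECIST analysis would expose the discrepancy. With no new lesion, the total tumor burden is the target sum, so a missed subject would be irPD at day 169 under the SAP's own nadir rule. The confirmation requirement in Protocol 8.6 covers only irPD at 12 weeks or earlier. That would reveal the error but would not correct the primary result.

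The table is limited to target lesions, so leaving out non-target progression is not itself a fault.

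**Conclusion.** The concern holds: the SAP's RECIST progression row contradicts the protocol and its own irRECIST row, and it is wrong as written. Confidence is high on the textual conflict. The effect on the primary endpoint depends on whether progression is derived from lesion sums with this row, which the SAP leaves open.

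If it is, the bias favors the treatment, apart from the opposite effect of the missing 5 mm condition at reference sums below 25 mm. Its size cannot be fixed from the documents. The rejection probabilities of 0.072 and 0.135 assume a true rate of 25%, 41 evaluable subjects, one or two expected misclassified subjects and, for the Kaplan-Meier method, no censoring before Cycle 7. The point should be fixed because it concerns the event definition of the primary endpoint.

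**What to change.** Replace the target-lesion progression row in SAP 3.3.1 with the protocol's rule: an increase of at least 20% over the smallest sum on study (baseline included) and of at least 5 mm, or a new lesion. Add a reference to Protocol 8.5.3.2 for non-target progression. Add one sentence stating whether progression is taken from the recorded response or derived from lesion sums, and that in either case the protocol's RECIST 1.1 criteria govern radiological progression for 6-month PFS, PFS time and duration of response.

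The cost is one table row and one sentence, with no new data. Programming changes only if progression was to be derived from lesion sums. N = 41 and the 16/41 threshold are unaffected.
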